4.3.2. Subject Discontinuation

The investigator has the right to discontinue a subject from study treatment or withdraw a subject from the study. In addition, subjects have the right to voluntarily discontinue study treatment or withdraw from the study at any time at his/her request for any reason.

In instances where a subject discontinues study treatment early, the investigator should strongly encourage the subject to continue the study and complete all scheduled visits, including any standard of care treatment. The site should continue to obtain vital status at Day 14 and Day 28 even if the subject withdraws consent. Rescue antibiotics are to be given to the subject as judged by the investigator. The discontinuation of study treatment will be registered in the IXRS.

Subjects who discontinue study treatment early and complete all scheduled visits will be considered study completers. If the subject is unwilling or unable to attend the scheduled site visits after hospital discharge, every effort should be made by the investigator (or qualified designee) to obtain data for the visits by either telephone, telemedicine, and/or home health visit.

Reasons for discontinuation of study treatment may include, but are not limited to:

- Insufficient therapeutic effect of the study drug (i.e., requirement for additional non-study antibacterial therapy to treat HABP/VABP based on the investigator's clinical judgment)
- AEs requiring discontinuation (e.g., hypersensitivity reactions based on investigator's clinical judgment)
- Any of the following post-baseline elevations in liver transaminase levels:
 - ALT or aspartate aminotransferase (AST) $\geq 8 \times$ ULN
 - ALT or AST $\geq 3 \times$ ULN, accompanied by total bilirubin $> 2 \times$ ULN OR international normalized ratio > 1.5
 - ALT or AST $\geq 3 \times$ ULN, accompanied with signs and symptoms compatible with hepatitis.
- 
- Pregnancy
- Important protocol deviation (i.e., affecting the subject's safety) as judged by the investigator
- Investigator or sponsor determines it is in the best interest of the subject
- Subject withdrawal of consent to receive further study treatment.

Reasons for withdrawal from the study may include, but are not limited to:

- Subject, or his or her legally authorized representative, withdrawal of consent
- Subject lost to follow-up
- Death
- Study termination by the Sponsor, or investigator decision, or by regulatory authorities.

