3.2.8. Clinically Evaluable (CE) Population

All subjects from the MITT who receive at least 72 hours of IV study treatment, have an appropriate diagnosis of HABP/VABP, have no important protocol deviations that would affect the assessment of clinical outcome, and have no missing nor indeterminate assessment of clinical outcome.

Based on the above definition, subjects who meet all of the following criteria will be included in the CE population:

- Duration of exposure to study drug ≥ 72 hours .
- Meets Inclusion Criterion 4: Has HABP or VABP, as defined below, requiring intravenous antimicrobial therapy. Note: HABP is defined as symptoms of acute bacterial pneumonia occurring at least 48 hours after hospitalization or within 7 days of discharge from an acute or chronic care facility (e.g., long term care, rehabilitation center, hospital or skilled nursing home). Subjects may have developed acute respiratory failure requiring mechanical ventilation for HABP (vHABP). VABP is defined as acute bacterial pneumonia for which the subject has received mechanical ventilation via endotracheal (or transnasal tracheal) intubation or tracheotomy for ≥ 48 hours.
- Subjects who do not meet Exclusion Criterion 2: Subjects with known or suspected community-acquired bacterial pneumonia, atypical pneumonia, viral pneumonia including novel coronavirus pneumonia (COVID-19), or chemical pneumonia (including

aspiration of gastric contents, inhalation injuries).

- No sustained discontinuation of the test drug \geq for 48 hours (if discontinued and total number of discontinuations < 8).
- No co-prohibition of systemic gram-negative antibiotics for \geq 72 hours (screened based on concomitant medication and co-prohibition regimen deviation data).
- No EOT or TOC Clinical Assessments Uncertain/Missing (Clinical Assessments at EOT and TOC visits may not be Uncertain or Missing. Note: Death resulting in a clinical assessment not being collected is not considered missing).

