3.2.9. Microbiologically Evaluable (ME) Population

All subjects in micro-MITT who received at least 72 hours of intravenous study treatment, had an appropriate diagnosis of HABP/VABP, had no significant protocol deviations that could affect the microbiologic efficacy evaluation, and had no microbiologic efficacy evaluations that were missing or inconclusive.

Based on the above definition, subjects who meet all of the following criteria will be included in the ME population:

- Eligible for micro-MITT population.
- Duration of exposure to the study drug \geq 72 hours.
- Meets Inclusion Criterion 4: Has HABP or VABP, as defined below, requiring intravenous antimicrobial therapy. Note: HABP is defined as symptoms of acute bacterial pneumonia occurring at least 48 hours after hospitalization or within 7 days of discharge from an acute or chronic care facility (e.g., long term care, rehabilitation center, hospital or skilled nursing home). Subjects may have developed acute respiratory failure requiring mechanical ventilation for HABP (vHABP). VABP is defined as acute bacterial pneumonia in subjects receiving mechanical ventilation via endotracheal (or transnasal tracheal) intubation or tracheotomy for ≥ 48 hours.
- Subjects who do not meet Exclusion Criterion 2: Subjects with known or suspected community-acquired bacterial pneumonia, atypical pneumonia, viral pneumonia including novel coronavirus pneumonia (COVID-19), or chemical pneumonia (including aspiration of gastric contents, inhalation injuries).
- No sustained discontinuation of the test drug \geq for 48 hours (if discontinued and total number of discontinuations < 8).
- No co-prohibition of systemic gram-negative antibiotics for \geq 72 hours (screened based on concomitant medication and co-prohibition regimen deviation data).
- No EOT or TOC microbiologic evaluations are indeterminate/missing (Evaluation of microbial efficacy at EOT and TOC visits may not be indeterminate/missing. (Note:

Lower respiratory tract samples are not collected at the EOT/TOC/LFU visit, and microbial efficacy is assessed on the basis of clinical efficacy results and is not missing).

- Only pathogenic bacteria identified in lower respiratory tract samples were considered.

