8.2. Secondary Efficacy Endpoint

The secondary endpoints for this study are the following:

- Day 28 all-cause mortality rate in the MITT population
- Day 14 and Day 28 all-cause mortality rate in the micro-MITT, extended micro-MITT, CE, ME, and CR-MITT populations
- The proportion of subjects with clinical success as evaluated by the investigator at Day 4, EOT, TOC, and LFU visits in the MITT, micro-MITT, extended micro-MITT, CE, ME, and CR-MITT populations
- The proportion of subjects with microbiological success at EOT, TOC, and LFU visits in the micro-MITT, extended micro-MITT, CR-MITT, and ME populations
- The proportional of subjects with microbiological success by pathogen at EOT, TOC, and LFU visits in the micro-MITT, extended micro-MITT, ME, and CR-MITT populations.
- The proportion of subjects with overall success at EOT, TOC, and LFU visits in the micro-MITT, extended micro-MITT, ME, and CR-MITT populations.

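### In CE, and less so in ME, the rule requiring EOT and TOC outcomes removes some known survivors but spares most otherwise eligible deaths, which distorts the secondary Day 14 and Day 28 mortality comparisons

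*SAP*

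**What the plan says.** SAP 3.2.8 sets several conditions for CE. One is minimum exposure: "Duration of exposure to study drug ≥ 72 hours". Another concerns outcome data: "Clinical Assessments at EOT and TOC visits may not be Uncertain or Missing". A note then exempts one cause of missingness: "Death resulting in a clinical assessment not being collected is not considered missing".

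SAP 3.2.9 sets parallel conditions for ME, including 72 hours of exposure and determinate outcomes: "Evaluation of microbial efficacy at EOT and TOC visits may not be indeterminate/missing". It has no note on death, but it does say that when no respiratory sample is taken, "microbial efficacy is assessed on the basis of clinical efficacy results and is not missing". SAP 8.2.2 counts death as a clinical failure and SAP 8.2.3.3 counts it as a microbiological failure, so in ME too a death gives a determinate outcome.

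SAP 8.2 lists as a secondary endpoint the "Day 14 and Day 28 all-cause mortality rate in the micro-MITT, extended micro-MITT, CE, ME, and CR-MITT populations". SAP 8.2.1.1 analyses these in the way of the primary endpoint. No separate CE or ME set is defined for mortality. TOC falls on Day 21 (± 2 days).

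Protocol 4.3.2 provides for vital status regardless of visit attendance: "The site should continue to obtain vital status at Day 14 and Day 28 even if the subject withdraws consent".

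**The concern.** For clinical success the death exemption is sensible: a death is a failure and should not leave the denominator. For mortality the same rule makes membership depend on the outcome being measured. Part of the selection also happens at Day 21, after the Day 14 endpoint has been determined.

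A subject who dies before the visit is kept. A subject recorded as alive on Day 14 and Day 28 who missed TOC, or was rated indeterminate, is removed, although that subject's mortality outcome is known. If visit attendance or indeterminate ratings differ between arms, the CE and ME mortality difference moves even when the drugs are equal.

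**Working it through.** **1. The plan's own figure.** SAP 1.3 assumes 10% mortality in both arms, 2:1 allocation of 450 subjects (300 vs 150), a 10-point margin and one-sided 0.025. The standard error is √(0.09/300 + 0.09/150) = 0.030, and power is Φ(0.10/0.030 − 1.96) = 91.5%. This agrees with the stated power of more than 90%. The documents give no size for CE or ME and no expected rate of missing or indeterminate EOT or TOC assessments, so the loss rates below are assumptions.

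**2. Who stays in CE.** All subjects below meet every other criterion, including 72 hours of exposure.

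| Subject | In CE? |
|---|---|
| Dies on Day 10, before EOT | Yes |
| Determinate EOT, then dies before Day 14 | Yes |
| Alive at Day 28, TOC missed | No |
| Alive at Day 28, EOT or TOC indeterminate | No |
| EOT missing or indeterminate for another reason, dies later | No |
| TOC missed for another reason, then dies by Day 28 | No |

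For Day 14, a survivor can be lost at EOT or at TOC. A death before EOT cannot be lost through this rule, and a death between EOT and Day 14 can be lost only at EOT. For Day 28, deaths after a missed TOC are lost as well, so the asymmetry is weaker. In ME, a survivor is lost through this criterion only when both the culture and the clinical outcome are absent, so fewer are lost.

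**3. Formula.** Let p be true mortality, d the share of survivors removed by this criterion and f the share of deaths removed for any reason. Expected mortality in the selected set is

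p(1 − f) / [p(1 − f) + (1 − p)(1 − d)].

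**4. The criterion alone (f = 0), equal loss in both arms, p = 10%.**
- d = 5%: 0.10/0.955 = 10.5%
- d = 10%: 0.10/0.910 = 11.0%
- d = 15%: 0.10/0.865 = 11.6%
- d = 20%: 0.10/0.820 = 12.2%

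**5. Unequal loss (f = 0), true difference zero, test minus control.**
- p = 10%, loss 15% vs 5%: 11.56% − 10.47% = +1.1 points. Reversing the loss gives −1.1.
- p = 15%, loss 15% vs 5%: 0.15/0.8725 − 0.15/0.9575 = 17.19% − 15.67% = +1.5 points. Reversing gives −1.5.
- p = 10%, loss 25% vs 5%: 12.90% − 10.47% = +2.4 points.

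Suppose the 10-point margin were applied to the CE result at p = 10%, starting from 300 vs 150 with no other exclusions. The approximate chance of meeting it would be 79% with 15% vs 5% loss and 91% with the loss reversed.

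**6. Counterweight from removed deaths (p = 10%, d = 10%).**
- f = 5%: 0.095/0.905 = 10.5%
- f = 10%: 0.090/0.900 = 10.0%
- f = 20%: 0.080/0.890 = 9.0%

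The net shift from the MITT rate is upward if f < d, zero if f = d and downward if f > d.

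**The case against.** The strongest reply is that the rule does not simply keep the dead and drop the living. A reader might infer that every death stays in and that CE and ME mortality must therefore exceed MITT mortality. The documents do not support either inference. The exemption covers only assessments missed because of death, so the last two rows of the table are deaths that the rule removes. The 72-hour requirement removes early deaths. The exclusion for 72 hours or more of prohibited Gram-negative antibiotics may remove failing patients. Step 6 shows that these can cancel or reverse the shift. Excluding patients with life expectancy under 3 days limits early deaths but does not rule them out. This part of the reply stands.

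A reader might also take CE and ME mortality as a per-protocol check on the non-inferiority claim. Neither document gives them that role. The sensitivity analyses in SAP 8.1.2.2 are multiple imputation and survival methods, and the primary decision rests on MITT.

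The loss rates are hypothetical and the resulting differences are small beside a standard error of about 3 points. The trial is double-blind. Protocol 4.3.2 asks sites to recover visits remotely, and Protocol 4.3.3 lets a late TOC count. SAP 3.2 fixes membership before the unblinded analysis and reports exclusions with their primary reason by arm. These points limit the likely size and make an imbalance visible, but reporting the exclusions does not correct the estimate.

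Finally, dropping the criterion has a cost of its own. SAP 8.1.2.1 and Section 11 count unknown survival as not dead, and the readmitted subjects are those most likely to lack vital status. The protocol says only that sites should obtain it. This stands, and the fix has to deal with it.

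**Conclusion.** The concern holds in a limited form. For Day 14 and Day 28 mortality, the EOT/TOC criterion selects partly on the outcome. Taken alone it raises mortality, most clearly at Day 14 and more in CE than in ME. Unequal loss of survivors can create a false difference of either sign: about 1.1 points at 10% mortality and 1.5 points at 15% mortality, for an assumed 15% vs 5% loss with no deaths removed. The larger figure is about 15% of the 10-point margin.

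The net direction against MITT cannot be stated, because it depends on how many deaths the 72-hour and other criteria remove. The primary analysis, and mortality in micro-MITT, extended micro-MITT and CR-MITT, are unaffected. The change is worth making because the exclusion is not needed to determine mortality in subjects whose vital status is known.

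**What to change.** In SAP 3.2.8, 3.2.9 and 8.2.1.1, state that the criterion on missing or indeterminate EOT and TOC outcomes is not applied when Day 14 and Day 28 mortality are analysed in CE and ME. Keep all other membership criteria, and keep this one for the clinical, microbiological and overall success endpoints.

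Report by arm how many subjects are readmitted and how many of them have unknown vital status at each time point. Add a check restricted to subjects with known vital status, because unknowns are otherwise counted as not dead.

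Protocol 8.2 carries the same requirement in its CE and ME definitions, so record the departure in SAP Section 11, or in the CSR if the SAP is already final.

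The cost is one extra population flag, plus a footnote because CE and ME denominators will differ between the mortality and success tables. The other post-randomization criteria remain, so the result is still a selected comparison, but no longer one selected through this rule.

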3.2.9. Microbiologically Evaluable (ME) Population

All subjects in micro-MITT who received at least 72 hours of intravenous study treatment, had an appropriate diagnosis of HABP/VABP, had no significant protocol deviations that could affect the microbiologic efficacy evaluation, and had no microbiologic efficacy evaluations that were missing or inconclusive.

Based on the above definition, subjects who meet all of the following criteria will be included in the ME population:

- Eligible for micro-MITT population.
- Duration of exposure to the study drug \geq 72 hours.
- Meets Inclusion Criterion 4: Has HABP or VABP, as defined below, requiring intravenous antimicrobial therapy. Note: HABP is defined as symptoms of acute bacterial pneumonia occurring at least 48 hours after hospitalization or within 7 days of discharge from an acute or chronic care facility (e.g., long term care, rehabilitation center, hospital or skilled nursing home). Subjects may have developed acute respiratory failure requiring mechanical ventilation for HABP (vHABP). VABP is defined as acute bacterial pneumonia in subjects receiving mechanical ventilation via endotracheal (or transnasal tracheal) intubation or tracheotomy for ≥ 48 hours.
- Subjects who do not meet Exclusion Criterion 2: Subjects with known or suspected community-acquired bacterial pneumonia, atypical pneumonia, viral pneumonia including novel coronavirus pneumonia (COVID-19), or chemical pneumonia (including aspiration of gastric contents, inhalation injuries).
- No sustained discontinuation of the test drug \geq for 48 hours (if discontinued and total number of discontinuations < 8).
- No co-prohibition of systemic gram-negative antibiotics for \geq 72 hours (screened based on concomitant medication and co-prohibition regimen deviation data).
- No EOT or TOC microbiologic evaluations are indeterminate/missing (Evaluation of microbial efficacy at EOT and TOC visits may not be indeterminate/missing. (Note:

Lower respiratory tract samples are not collected at the EOT/TOC/LFU visit, and microbial efficacy is assessed on the basis of clinical efficacy results and is not missing).

- Only pathogenic bacteria identified in lower respiratory tract samples were considered.

3.2.10. Pharmacokinetic (PK) Population

All subjects from the SAF during the study with at least 1 reportable concentration of XNW4107, imipenem, or cilastatin.

The PK population was judged only for the study drug treatment group.

3.3. Subject Grouping

When analysis is performed based on the ITT, MITT populations, subjects will be grouped according to the treatment they were randomized to receive. For analyses based on the SAF, micro-MITT, CR-MITT, extended micro-MITT, CE, ME, and PK populations, subjects will be grouped according to the treatment they actually received. The actual treatment group received will differ from the randomly assigned treatment group only if all of the study or control medications actually received by the subject throughout the treatment period are different from the randomly assigned medications.

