3.2.4. Microbiologic Modified Intent-to-Treat (micro-MITT) Population

The micro-MITT population is defined as all subjects from the MITT who have a Gram-negative pathogen identified at baseline and the pathogen is susceptible to the investigational medicinal product and comparator.

For cases where multiple gram-negative pathogens (plural organisms) were identified at baseline, all pathogens were only included in micro-MITT if they were susceptible to the test and control drugs.

Only pathogenic bacteria identified in lower respiratory tract samples were considered.

The rules for the processing and derivation of microbiological data, as well as related definitions, are detailed in Section [3.6.2](#).

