3.2.5. Carbapenem-resistant Modified Intent-to-Treat (CR-MITT) Population

All subjects from the MITT who have a baseline Gram-negative pathogen identified which is resistant to any carbapenem.

Any one pathogen resistant to any carbapenem antibiotic can be included in the CR-MITT population.

Only pathogenic bacteria identified in lower respiratory tract samples were considered.

The rules for the processing and derivation of microbiological data, as well as related definitions, are detailed in Section [3.6.2](#).

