3.2.6. Extended Microbiologic Modified Intent-to-Treat (extended micro-MITT) Population

All subjects from the MITT who have a baseline Gram-negative pathogen identified which is susceptible to either the investigational medicinal product or comparator.

Gram-negative pathogens identified in the extended micro-MITT population need to have at least one susceptible to the test drug or control drug.

Only pathogenic bacteria identified in lower respiratory tract samples were considered.

The rules for the processing and derivation of microbiological data, as well as related definitions, are detailed in Section 3.6.2.

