8.1.2.4. Subgroup Analysis

Day 14 all-cause mortality will be analyzed in the MITT population for the following subgroups

- Age (< 65 and \geq 65)
- Gender (male and female)
- Country/region (China and the rest of the world)
- Type of infection at baseline (non-ventilated HABP and ventilated HABP)
- Baseline APACHE II scores (<15 and \geq 15)
- ICU admission at baseline (yes/no)
- Baseline eGRF classification (<30 mL/min, 30 to <60 mL/min, 60 to <90 mL/min, 90 to <150 mL/min, 150 to <250 mL/min and \geq 250 mL/min)
- Baseline liver function (normal, abnormal)
- Received antimicrobial therapy for this HABP/VABP (yes/no)
- Whether the subject's prior antibiotic therapy was considered a clinical treatment failure (yes/no)
- Baseline lower respiratory tract gram-negative infections (mono/poly)

- Top 5 Ranking of Respiratory Gram-Negative Bacteria under Baseline HABP/VABP (5 most frequent in combined dose groups)
- Resistance to gram-negative pathogenic bacteria of the respiratory tract at baseline (carbapenem-resistant/non-resistant)
- Concomitant bacteremia at baseline (yes/no)

For a subject, if the value of the grouping variable cannot be determined, this subject will be excluded from the corresponding subgroup analysis. Non-stratified risk difference between treatment groups will be evaluated for each of the subgroups. A forest plot will graphically present the non-stratified risk difference and 95% CI using normal approximation with a continuity correction on the treatment differences in the all-cause mortality rates at Day 14 between IMI-XNW4107 and IMI/REL for each of the subgroups. For both treatment groups, subjects with unknown survival at Day 14 will not be considered dead.

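### SAP 3.3 groups MITT as randomised but micro-MITT, CR-MITT and extended micro-MITT, which are MITT subsets chosen only on baseline microbiology, as treated

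*SAP*

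**What the plan says.** SAP 3.3 sets two rules. ITT and MITT follow the randomised arm. SAF follows the drug received, and so do the other sets it names: for the "micro-MITT, CR-MITT, extended micro-MITT, CE, ME, and PK populations, subjects will be grouped according to the treatment they actually received". The rule then narrows what counts as a change of arm: "The actual treatment group received will differ from the randomly assigned treatment group only if all of the study or control medications actually received" over the whole treatment period differ from the assigned drug. Mixed dosing moves nobody. No reason is given for where the line between the two rules falls.

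The definitions of three of the as-treated sets rest on MITT membership plus baseline microbiology:

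- micro-MITT (3.2.4): "all subjects from the MITT who have a Gram-negative pathogen identified at baseline", with susceptibility to both drugs.
- CR-MITT (3.2.5): "All subjects from the MITT who have a baseline Gram-negative pathogen identified which is resistant to any carbapenem".
- Extended micro-MITT (3.2.6): MITT subjects with a "baseline Gram-negative pathogen identified which is susceptible to either the investigational medicinal product or comparator".

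CE (3.2.8) and ME (3.2.9) differ in kind. They add conditions that arise after randomisation: at least 72 hours of treatment, limits on interruptions and prohibited antibiotics, and an evaluable outcome.

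The same endpoints are reported on both sides of the line. SAP 8.2 lists "Day 14 and Day 28 all-cause mortality rate in the micro-MITT, extended micro-MITT, CE, ME, and CR-MITT populations" alongside the MITT mortality analyses, and 8.2.1.1 analyses them in a manner similar to the primary endpoint.

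Protocol 8.2 states a grouping rule only for ITT (as randomised) and SAF (as treated). It is silent on the sets at issue.

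**The concern.** A set formed by selecting randomised and dosed subjects on a baseline characteristic keeps the benefit of randomisation as long as its members are compared by assigned arm. Grouping by drug received gives that up for any subject whose drug differs from assignment, and these three sets have no exposure or compliance condition that would explain doing so.

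The practical sign would be tables that do not nest. Take Day 14 mortality in carbapenem-resistant subjects. Section 8.1.2.4 tabulates it within MITT, under the subgroup "Resistance to gram-negative pathogenic bacteria of the respiratory tract at baseline (carbapenem-resistant/non-resistant"), as randomised. Section 8.2 tabulates it again in CR-MITT, as treated. The two use different estimators (unstratified and stratified), so the differences need not match. If both use the resistance definition in 3.6.2, however, the numbers of subjects and deaths per arm should agree, and with one fully misallocated subject they would not.

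Mortality and clinical success also have as-randomised results in MITT. Microbiological and overall success are not analysed in MITT, so for them the subset analyses are the main results.

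**Working it through.** **No plan figure to reproduce.** The plan gives no figure for this rule, no subset sizes and no count of misallocated subjects. The sample-size statement (SAP 1.3) concerns the primary comparison and is not affected: 0.10/√[0.1×0.9×(1/300+1/150)] − 1.96 = 3.33 − 1.96 = 1.37, a power of 91.5%, consistent with the stated figure of more than 90%.

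**Step 1: which tables the rule reaches.** By-subject secondary comparisons in the three sets (SAP 8.2, 8.2.1.1, 8.2.2.1, 8.2.3.3, 8.2.4.1):

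| Endpoint | Sets × times | Comparisons | Also analysed in MITT (as randomised)? |
|---|---|---|---|
| Mortality | 3 × 2 | 6 | yes |
| Clinical success | 3 × 4 | 12 | yes |
| Microbiological success | 3 × 3 | 9 | no |
| Overall success | 3 × 3 | 9 | no |
| Total | | 36 | |

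The rule also reaches the by-pathogen and MIC tables (8.2.1.3, 8.2.2.3, 8.2.3.5, 8.2.4.3), the micro-MITT demographic and baseline tables (5.1, 5.2), and the baseline pathogen and MIC summaries in 5.2.

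Among the populations that 3.3 lists, the last two endpoint rows (9 + 9 comparisons) have no as-randomised analysis. For the 9 microbiological comparisons this is conditional. Section 8.2.3.3 also analyses extended micro-MITT 2, which 3.3 does not name and whose definition is not visible in the public copy. If that set is grouped as randomised, microbiological success would have one such analysis. Overall success (8.2.4.1) is not planned in that set, so its 9 comparisons do not depend on this.

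**Step 2: effect of moving one subject.** Inputs:

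- Estimator from SAP 8.1.2.1: Σ W_h d_h / Σ W_h, with W_h = n1h·n2h/(n1h+n2h).
- Four strata, infection type × APACHE II, because SAP 11 drops region.
- CI from the SAP variance terms, with the standard error divided by Σ W_h to match the estimator.
- Assumptions, not in the documents: subset sizes, stratum split, 20% mortality and 60% success. The 10% mortality rate is the design rate. Arms start equal, so the difference is 0 before the move.

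Strata (test/control) are 20/10, 10/5, 10/5, 20/10 for 60 vs 30, and 60/30, 40/20, 40/20, 60/30 for 200 vs 100. Shifts are in percentage points:

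| Move | 60 vs 30, mortality 20% | 200 vs 100, mortality 10% |
|---|---|---|
| Survivor, control to test | −1.02 | −0.15 |
| Survivor, test to control | +0.99 | +0.15 |
| Death, control to test | +4.07 to +4.08 | +1.36 |
| Death, test to control | −3.94 to −3.95 | −1.34 |
| 95% CI half-width before the move | 19.6 | 7.7 |

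An unstratified check for 60 vs 30 (12 and 6 deaths) gives 13/61 − 5/29 = +4.07 for a control death moved to test, and 12/61 − 6/29 = −1.02 for a control survivor moved to test.

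For microbiological success at 60%, one subject shifts the difference by −3.06 to +2.96 points (60 vs 30; half-width 22.9) or by −0.90 to +0.90 points (200 vs 100; half-width 12.0).

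**Step 3: direction.** With equal true rates, the expected shift for a control subject moved to test (60 vs 30 at 20%) is 0.2 × 4.07 + 0.8 × (−1.02) = 0.0. There is no built-in tilt towards either arm.

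**The case against.** The strongest reply is that SAP 3.3 is explicit and pre-specified, contradicts nothing in the protocol, and needs a rare event before it matters. All of that is true, and it keeps the point minor.

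There is also a case for grouping by drug received. The SAP tabulates outcomes in these sets by the baseline MIC of each drug. A fully misallocated subject grouped as randomised would be shown against the MIC of a drug never given. In a non-inferiority setting, grouping such subjects as randomised also pulls the arms together. The SAP offers neither argument. The first applies to the MIC listings, not to comparisons of mortality or success, and a flag in those listings meets it. The second would apply equally to MITT, where the SAP uses randomised arms for its primary non-inferiority test.

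A further reply is that the change moves the mismatch elsewhere. ME requires that a subject be "Eligible for micro-MITT population", and both sets are now grouped as treated, so they agree. Baseline tables are produced for the Safety and micro-MITT populations, which also agree now. This stands as a small cost. It is the familiar difference between a randomised set and an evaluable or safety set, and it can be stated openly.

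A reader might infer more than the documents support:

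- That the primary result is at risk. It is not, because MITT is grouped as randomised.
- That the SAP departs from the protocol. It does not, because the protocol gives no rule for these sets.
- That misallocation happened. No case is reported.
- That all 18 microbiological and overall comparisons certainly lack an as-randomised analysis. For the 9 microbiological ones this depends on extended micro-MITT 2.
- That a 4-point shift is typical. It is the effect of a misallocated death in a small set at 20% mortality. SAP 14 describes mortality in the trial as low, so a misallocated survivor is the likelier case.

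**Conclusion.** The inconsistency is real and minor. Three sets defined by MITT membership and baseline microbiology are grouped under the rule used for safety, PK and evaluable sets, with no reason given. Their comparisons would stop following randomisation for any subject who received only the non-assigned drug.

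The effect is exactly zero if there is no such subject. If there is one, the assumed sizes above put the shift at between 0.15 and about 4 points for mortality, and at up to about 3 points for microbiological success. Each shift is well inside the CI half-width. These figures rest on assumed subset sizes and rates, equal arms at the start and a single misallocated subject. More such subjects or smaller subsets would give larger shifts.

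The case for acting is that a grouping rule should be right before anyone knows whether it moves a subject, and that overall success has no as-randomised analysis to fall back on.

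**What to change.** In SAP 3.3, move micro-MITT, CR-MITT and extended micro-MITT to the as-randomised rule, alongside ITT and MITT. Keep actual treatment for SAF and PK, which agrees with the listing convention in 3.1. If CE and ME stay as treated, say that this is a deliberate per-protocol-type choice. In the MIC-response listings, flag any fully misallocated subject with the drug actually received.

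The cost is one rewritten sentence and a check of the affected table specifications, including the micro-MITT demographic and baseline tables. No new data are needed, and sample size, power and the primary analysis do not change. The remaining downside is that a misallocated subject could then differ in arm between micro-MITT and ME or Safety tables, which a footnote can cover. If the SAP is already final, SAP 1 requires the change to be documented in the CSR.
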